8. BIOSPECIMEN STUDIES AND PROCEDURES

The correlative research proposed below represents ideas based upon the state of the field to date. However, the exact correlative research that will be done may be modified based upon the sample availability and best science at the time these assays are ready to be performed. The correlative laboratory manual (CLM) will contain detailed instructions regarding correlatives.

8.1 Archival Tissue

Archival tissue is required if available. If archival tissue is not available, the subject may still be eligible for the trial. Archival tissue should be identified and requested at screening and shipped by Cycle 2 Day 1, if available.

8.3.2 Tumor Immune Infiltrates by Immunohistochemistry (IHC)

Tumor samples may be tested by IHC for expression of proteins that may be associated with sensitivity or resistance to atezolizumab, including but not limited to immune cell populations including CD3, CD4, CD8, Treg, Th17 T-cells and monocyte/macrophage and neutrophil populations, as well as immune and tumor cell expression of PD-1, and PD-L1 and PD-L2, respectively. Multiplex IHC opportunities could be performed by Genentech or other laboratory upon receipt of adequate funding.

8.1.2 Tumor Immune/Inflammatory Analysis by Gene Expression

RNASeq may be conducted in order to assess gene expression of the tumor. Analyses could be conducted by Genentech or other laboratory upon receipt of adequate funding.

8.1.3 Characterization of genomic alterations by whole exome sequencing

Whole exome sequencing or specific targeted DNA panels may be conducted. Analyses could be conducted by Genentech or other laboratory upon receipt of adequate funding.

8.2 Peripheral Blood Samples

Blood (whole blood for PBMCs, plasma and buffy coat) for correlative analysis will be drawn prior to treatment on Cycle 1 Day 1, Cycle 3 Day 1 and at the D30 safety visit/progression.

8.2.1 Circulating Immune Cell Analysis

Immune cell correlates using flow-based assays may be performed in collaboration with the Duke Immune Profiling Core (DIPC) laboratory. Changes in the immune cell subtypes that are expected to be altered by treatment will be analyzed. Other technologies approaches may also be considered. The lymphoid panel focuses on T-cell activation, maturation, regulation, and exhaustion. The myeloid panel focuses on myeloid derived suppressor cells (MDSC), M1/M2 polarization, and dendritic cells (DC, pDC).

8.2.2 Circulating Protein Analysis

Analyses may include immune proteins, inflammatory cytokines and tumor growth factors upon receipt of adequate funding. Analyte levels, and changes in analyte levels, will be correlated with clinical outcome (PFS, OS). Plasma may be evaluated for protein markers that may be associated with sensitivity or resistance to atezolizumab. These may include CRP and other markers of inflammation, including but not limited to IFN γ , IL1 β , IL4, IL6, IL7, IL10, IL12, IL17A, IL17E, and IL23.

8.2.3 Cell-free DNA for mutational analysis

Tumor-derived cfDNA (ctDNA) has become the focus of intensive investigation in the search for genomic biomarkers that can be used to monitor the presence or absence of disease, disease progression, or the development of resistance mechanisms during the course of treatment. The promise of cfDNA is that it may provide a sensitive and non-invasive means of monitoring the genetic composition of a patient's disease both during treatment and as a means of monitoring response or resistance. ctDNA analysis may be performed upon receipt of adequate funding. The final gene panel will be decided at the time of analysis, allowing for coverage of the most relevant point mutations, amplifications, and gene fusions.

8.2.4 Buffy Coat for Germline DNA

Buffy coat will be collected for germline DNA samples. These samples may be used as a somatic baseline comparison when analyzing ctDNA and/or tumor mutations.

8.2.5 Exosome Analysis

Exosomes are composed of numerous RNA, proteins, lipids and have great biomarker potential, as they transport molecular contents of cells from which they originate. Additional analysis of exosomes may also be performed upon receipt of adequate funding.

8.3 Genetic Testing

Participants will be given information as part of the informed consent process that samples will be used for research purposes that will include genetic testing. The intent is not to give participants (or his/her medical providers) the results of any testing done for research purposes; however, incidental germline (inheritable) mutations may be identified of which a participant may or may not already be aware. In the case where an incidental genetic finding is identified, the sponsor investigator of this project will be notified. Possible decisions for handling incidental findings may include notification of the participant (and provider); recommendation for genetic counseling, which may or may not include genetic testing (e.g., if the finding was not done in a CLIA certified laboratory); or, neither. In general, a member of the participant's treating team will be given the information to help with notification. In all cases, the current policy of Duke University Medical Center and local/participating site IRBs, as applicable, will be followed. Any additional approvals that may be required prior to participant notification will be secured in advance.

8.4 Banking of Leftover Biospecimens

Subject consent will be obtained to bank any leftover samples collected for study-specific correlative research. Hoosier Cancer Research Network (HCRN) will manage the banked samples. Samples will be coded and banked indefinitely in the Hoosier Cancer Research Network Biorepository and used for future unspecified cancer-related research.

8.5 Confidentiality of Biospecimens

Samples will be identified by the subject's study number assigned at the time of registration to the trial. Any material issued to collaborating researchers will be anonymized and only identified by the subject's study number.

8.6 Quality of Life Assessment

8.6.1 Patient Reported Outcomes

Quality of life evaluations include FACT-Br, FACIT-Fatigue, and Godin Leisure-Time Exercise Questionnaire. These questionnaires are to be completed Cycle 1 Day 1 then every other Cycle of treatment (6 weeks; ± 1 week).

Patient-reported Quality of Life (QoL) outcomes will be assessed using the following standardized and validated questionnaires:

- Functional Assessment of Cancer Therapy-Brain (FACT-BR) scale (version 4) [26], which contains subscales for physical (7-items), functional (7-items), emotional (6-items), and social/family (7-items) well-being, as well as a 23-item brain cancer subscale (BCS) that assesses symptoms commonly reported by brain cancer patients
- Functional Assessment of Cancer Therapy-Fatigue (FACIT-Fatigue) subscale (version 4) [27]
- Godin Leisure-Time Exercise Questionnaire Short Scale [28, 29], a simple questionnaire to assess patterns of exercise behavior during a subject's leisure time

9. CRITERIA FOR DISEASE EVALUATION

9.1 Definitions for Response Evaluation – RECIST 1.1

9.1.1 Measurable Disease

Measurable disease is defined as the presence of at least one measurable lesion. Measurable lesions are defined as those that can be accurately measured in at least one dimension (longest diameter to be recorded) as >20 mm by chest x-ray, as >10 mm with CT scan, or >10 mm with calipers by clinical exam. All tumor measurements must be recorded in millimeters (or decimal fractions of centimeters).

Malignant Lymph Nodes

To be considered pathologically enlarged and measurable, a lymph node must be >15 mm in short axis when assessed by CT scan (CT scan slice thickness recommended to be no greater than 5 mm). At baseline and in follow-up, only the short axis will be measured and followed.

9.1.2 Non-measurable Lesions

All other lesions (or sites of disease), including small lesions (longest diameter <10 mm or pathological lymph nodes with ≥ 10 to <15 mm short axis), are considered non-measurable disease. Bone lesions, leptomeningeal disease, ascites, pleural/pericardial effusions, lymphangitis cutis/pulmonitis, inflammatory breast disease, and abdominal masses (not followed by CT or MRI), are considered as non-measurable. **NOTE:** Cystic lesions that meet the criteria for radiographically defined simple cysts should not be considered as malignant lesions (neither measurable nor non-measurable) since they are, by definition, simple cysts. 'Cystic lesions' thought to represent cystic metastases can be considered as measurable lesions, if they meet the definition of measurability described above. However, if non-cystic lesions are present in the same subject, these are preferred for selection as target lesions.

9.1.3 Target Lesions

All measurable lesions up to a maximum of 2 lesions per organ and 5 lesions in total, representative of all involved organs, should be identified as target lesions and recorded and measured at baseline. Target lesions should be selected on the basis of their size (lesions with the longest diameter), be representative of all involved organs, but in addition should be those that lend themselves to reproducible repeated measurements. It may be the case that, on occasion, the largest lesion does not lend itself to reproducible measurement in which circumstance the next largest lesion which can be measured reproducibly should be selected. A sum of the diameters (longest for non-nodal lesions, short axis for nodal lesions) for all target lesions will be calculated and reported as the baseline sum diameters. If lymph nodes are to be included in the sum, then only the short axis is added into the sum. The baseline sum diameters will be used as reference to further characterize any objective tumor regression in the measurable dimension of the disease.

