2.2.2 Secondary Endpoints

- ORR will include complete response (CR) + partial response (PR) as determined by RECIST 1.1.
- Extracranial PFS is defined as the time from Day 1 of treatment until the criteria for extracranial disease progression is met as defined by RECIST 1.1 or death as a result of any cause, whichever comes first.
- OS is defined as the time from Day 1 of treatment until death as a result of any cause.
- Toxicity will be graded by Common Toxicity Criteria for Adverse Events (CTCAE V5).

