3. ELIGIBILITY CRITERIA

3.1 Inclusion Criteria

Subject must meet all of the following applicable inclusion criteria to participate in this study:

1. Written informed consent and HIPAA authorization for release of personal health information prior to registration. **NOTE:** HIPAA authorization may be included in the informed consent or obtained separately.
2. Age \geq 18 years with ability and willingness to provide informed consent.
3. ECOG Performance Status of 0-2.
4. Histological confirmation of Small Cell Lung Cancer- Extensive Stage (SCLC) per Veterans Administration Lung Study Group (VALG).
5. At least one untreated asymptomatic brain metastasis that is measurable by RECIST 1.1 that has not been previously irradiated.
6. No prior treatment for metastatic disease. **EXCEPTION:** A single cycle of chemotherapy (platinum/etoposide) with or without atezolizumab is allowed within 30 days prior to enrollment.
7. Treatment-free for at least 6 months since last chemo/radiotherapy, among those treated (with curative intent) with prior chemo/radiotherapy for limited-stage SCLC.
8. Any prior cancer treatment must be completed at least 6 months prior to registration and the subject must have recovered from all reversible acute toxic effects of the regimen (other than alopecia) to Grade \leq 1 or baseline. **NOTE:** a single cycle of chemotherapy (platinum/etoposide) with or without atezolizumab is allowed within 30 days prior to enrollment. **NOTE: Extracranial radiation is allowed.**
9. A concurrent diagnosis of a separate malignancy is allowed if clinically stable and does not require tumor-directed therapy.

10. Demonstrate adequate organ function as defined in the table below

System	Laboratory Value
Hematological	
Absolute Neutrophil Count (ANC)	2 1.5K/mm ³ without GCSF
Hemoglobin (Hgb)	2 9 g/dL (without transfusion)
Lymphocyte Count	2 500/ μ L
Platelet Count	2 100,000/ μ L without transfusion
Renal	
Calculated creatinine clearance	2 50 cc/min
OR	
Serum Cr	< 1.5 x institutional ULN
Hepatic	
Bilirubin	< 1.5 \times upper limit of normal (ULN)
Aspartate aminotransferase (AST)	< 2 \times ULN without liver metastasis < 5 \times ULN with liver metastasis
Alanine aminotransferase (ALT)	< 2 \times ULN without liver metastasis < 5 \times ULN with liver metastasis

¹ Cockcroft-Gault formula will be used to calculate creatinine clearance

² Patients with known Gilbert disease who have serum bilirubin level < 3x ULN may be enrolled

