6.4 Protocol Therapy Discontinuation

In addition to discontinuation from therapy related to toxicities as outlined above, a subject will also be discontinued from protocol therapy and followed per protocol under the following circumstances outlined below. The reason for discontinuation of protocol therapy will be documented on the electronic case report form (eCRF)

- Documented disease progression based on RECIST 1.1
- Site investigator determines a change of therapy would be in the best interest of the subject
- Subject requests to discontinue protocol therapy, whether due to unacceptable toxicity or for other reasons
 - In a subject decides to prematurely discontinue protocol therapy (“refuses treatment”), the subject should be asked if he or she may still be contacted for further scheduled study assessments. The outcome of that discussion should be documented in both the medical records and in the eCRF.
- Female subject becomes pregnant
- Protocol therapy is interrupted for ≥ 63 days.

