9.1.4 Non-target Lesions

All other lesions (or sites of disease) including any measurable lesions over and above the 5 target lesions should be identified as non-target lesions and should also be recorded at baseline. Measurements of these lesions are not required, but the presence, absence, or in rare cases unequivocal progression of each should be noted throughout follow-up.

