9.1.5 Evaluation of Target Lesions

NOTE: In addition to the information below, also see the international criteria proposed by the Response Evaluation Criteria in Solid Tumors (RECIST) Committee, version 1.1 (Eur J Cancer 45;2009:228-247) for special notes on the assessment of target lesions.

Complete Response (CR)	Disappearance of all target lesions. Any pathological lymph nodes (whether target or non-target) must have reduction in short axis to <10 mm.
Partial Response (PR)	At least a 30% decrease in the sum of the diameters of target lesions, taking as reference the baseline sum diameters
Progressive Disease (PD)	At least a 20% increase in the sum of the diameters of target lesions, taking as reference the smallest sum on study (this includes the baseline sum if that is the smallest on study). In addition to the relative increase of 20%, the sum must also demonstrate an absolute increase of at least 5 mm. (Note: the appearance of one or more new lesions is also considered progressions).
Stable Disease (SD)	Neither sufficient shrinkage to qualify for PR nor sufficient increase to qualify for PD, taking as reference the smallest sum diameters while on study

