9.2.2 Tumor response assessment

Assignment of CNS response is independent of systemic disease response. All baseline assessments should be done as close as possible to the treatment start and no more than 4 weeks before the beginning of treatment. When more than one measurable lesion in the CNS is present at baseline, all lesions up to a maximum of five CNS lesions should be identified as target lesions and will be recorded and measured at baseline. Target lesions should be selected on the basis of their size (longest diameter) and as those that can be measured reproducibly. A sum of the diameters for all target lesions will be calculated and reported as the baseline sum of longest diameters. All other CNS lesions should be identified as non-target lesions and should also be recorded at baseline.

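### Extracranial PFS is scored by RECIST 1.1 rules that do not exclude the brain, so brain shrinkage can mask extracranial progression and brain growth can be scored as an extracranial event

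*Combined protocol and SAP*

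**What the plan says.** Extracranial PFS (section 2.2.2, secondary endpoints) runs from Day 1 of treatment "until the criteria for extracranial disease progression is met as defined by RECIST 1.1", or death. RECIST 1.1 is set out in section 9.1 as a whole-body system:

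- Targets (9.1.3): "All measurable lesions up to a maximum of 2 lesions per organ and 5 lesions in total, representative of all involved organs". One sum "for all target lesions will be calculated and reported as the baseline sum diameters".
- Non-targets (9.1.4): "All other lesions (or sites of disease) including any measurable lesions over and above the 5 target lesions should be identified as non-target lesions".
- Progression (9.1.5): a rise of 20% or more over the smallest sum on study, and of 5 mm or more. In addition, "the appearance of one or more new lesions is also considered progressions". The response table in 9.1.7 likewise puts no site limit on new lesions.

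Inclusion criterion 5 (section 3.1) requires "At least one untreated asymptomatic brain metastasis that is measurable by RECIST 1.1". Section 9.1.2 lists leptomeningeal disease among non-measurable lesions, so the RECIST text does reach into the CNS. Calendar footnote 5 (section 7) puts brain MRI and body CT in one tumor assessment.

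The brain is also scored by RANO-BM (section 9.2), with up to five CNS targets of its own. Section 9.2.2 states: "Assignment of CNS response is independent of systemic disease response".

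Section 12.2.2 defines PFS as progression in either compartment by RECIST 1.1 and RANO-BM together, and gives no extracranial-only definition. Section 6.4 ends protocol therapy on "Documented disease progression based on RECIST 1.1", without naming a compartment.

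**The concern.** An endpoint called extracranial should depend only on disease outside the brain. Here the criterion that defines it uses a lesion set that must represent every involved organ, and the brain is involved in every patient. Up to 2 of the 5 target slots can hold brain lesions, and no section defines an extracranial sum, nadir or new-lesion rule.

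Two errors of opposite direction follow. A brain response can hold down the pooled sum while extracranial disease progresses, so the event is recorded late or missed. Brain growth, or a new brain lesion, can produce a RECIST progression that is then entered as an extracranial event. One site may follow 9.1.3 to the letter and another may follow the evident intent, so identical scans could yield different event dates.

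**Working it through.** **Plan's own figures.** The plan gives none on this point. Its only design figure, about 81% power with 60 patients (section 12.3), concerns iPFS, which is defined by RANO-BM and does not use the RECIST lesion set. Nothing below changes it.

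**Does any section remove the brain from RECIST?** Sections 9.1.3, 9.1.4, 9.1.5 and 9.1.7 do not. Section 2.2.2 uses the word extracranial but leaves the criteria to RECIST 1.1. The independence sentence in 9.2.2 governs how CNS response is assigned; it does not take brain lesions out of the RECIST sum or the new-lesion rule. Section 12.2.2 does not settle it, because its PFS covers both compartments.

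**Formula.** Let s be the brain share of the reference sum, b the proportional change in the brain targets and e the change in the extracranial targets. Then

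pooled change = s·b + (1 − s)·e.

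The thresholds come from 9.1.5. All lesion sizes and shares are assumed, since the documents give none. Baseline is taken as the smallest sum, with no new lesion and no non-target progression.

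**Masking.** Extracranial 60 to 73 mm, brain 30 to 18 mm.

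- Extracranial alone: 73/60 − 1 = +21.7%, +13 mm. Progression.
- Pooled: (73 + 18)/(60 + 30) − 1 = 91/90 − 1 = +1.1%, +1 mm. Not progression.

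**Brain-driven progression.** Extracranial unchanged at 60 mm, brain 40 to 65 mm.

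- Extracranial alone: 0%. Not progression.
- Pooled: 125/100 − 1 = +25%, +25 mm. Progression.

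**Sensitivity to the brain share.** Setting the pooled change to +20% and solving gives e = (0.20 − s·b)/(1 − s). With b = −50% this is (0.20 + 0.50s)/(1 − s). With e = 0, the brain growth that reaches +20% unaided is b = 0.20/s.

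| Brain share of sum | Extracranial growth needed if brain shrinks 50% | Brain growth that alone reaches +20% |
|---|---|---|
| 20% | 37.5% | 100% |
| 30% | 50% | 67% |
| 40% | 67% | 50% |
| 50% | 90% | 40% |

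With the brain excluded, the extracranial growth needed is 20% in every row, and brain growth has no effect.

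**New lesions.** Under 9.1.5 a new lesion at any site is progression. Under 9.2.4 a new CNS lesion alone may not be progression during immunotherapy, and 9.2.5 asks for later confirmation in early cases without neurologic worsening. The same new brain lesion can therefore be progression at once under one section and not yet under the other.

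**The case against.** The strongest reply is that separation was plainly intended. Section 2.2.2 asks for extracranial progression, and a new brain lesion is not extracranial. Section 9.2 assigns the brain to RANO-BM, and 9.2.2 makes CNS response independent. A careful site would leave the brain out.

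Part of this stands. A reader might infer that every brain-only failure counts as an extracranial event. The documents do not support that, because the word extracranial lets a site decline to score it. What they support is that such an event may be scored, and inconsistently. The reply does not answer masking: the word extracranial supplies no separate sum, and 9.1.3 provides only the pooled one.

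Four other stronger readings also fail.

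- **A number of false events, or a shift in median PFS.** This needs the share of brain-only progressions and the scoring habits of sites, and the documents give neither. The two errors also pull in opposite directions.
- **ORR is wrong.** Sections 2.2.2 and 12.2.2 define an overall rate by RECIST 1.1, and whole-body scoring fits that. The plan need only say which is meant.
- **Small growth in brain targets is RECIST progression but clearly stable by RANO-BM.** The 5 mm single-lesion condition in 9.2.3 is absent from the 9.2.5 table, which lists a 20% rise as progression, so RANO-BM gives no clear answer.
- **The primary endpoint is compromised.** The iPFS definition does not use the RECIST lesion set. Section 6.4 could affect which later scans exist, but that depends on how it is read alongside 9.2, and the documents allow no estimate.

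**Conclusion.** The concern holds as a defect in the rules for one named secondary endpoint. As written, the RECIST lesion set behind extracranial PFS includes the brain. It can mask extracranial progression and can generate RECIST progressions from brain findings that may be entered as extracranial.

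Both mechanisms are arithmetically certain under the pooled sum; their frequency is unknown. The illustrations rest on assumed lesion sizes. Their effect grows with the brain share: if the brain shrinks by half, the extracranial growth needed to register rises from 20% to between 37.5% and 90% for shares of 20% to 50%.

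Brain-driven events distort only the extracranial PFS of section 2.2.2, since brain progression belongs in the either-compartment PFS of section 12.2.2. Masked extracranial growth can affect both. The iPFS definition and the sample size are untouched.

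**What to change.** State in 9.1.3 to 9.1.5 that, for extracranial PFS, RECIST 1.1 target, non-target and new lesions are restricted to sites outside the CNS, with their own baseline sum and nadir, and that CNS lesions are assessed by RANO-BM under 9.2. For the either-compartment PFS in 12.2.2, take the earlier of extracranial RECIST progression and RANO-BM CNS progression. State whether ORR is whole-body or extracranial; it need not be redefined.

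Section 6.4, which ends therapy on RECIST 1.1 progression without naming a compartment, must be reconciled with 9.2. No direction is proposed here.

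The cost is a few sentences and a derived extracranial sum, with no extra scans. There are two downsides. Patients without measurable extracranial disease can be followed only on non-target and new extracranial lesions. For patients already enrolled, extracranial lesions displaced from the five target slots by brain lesions may lack measurements, because 9.1.4 does not require them for non-targets. The analysis should report how many patients this affects.

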9.2.1 Measurable disease

Measurable disease is defined as a contrast-enhancing lesion that can be accurately measured in at least one dimension, with a minimum size of 10 mm, and is visible on two or more axial slices that are preferably 5 mm or less apart with 0 mm skip (and ideally ≤ 1.5 mm apart with 0 mm skip). Additionally, although the longest diameter in the plane of measurement is to be recorded, the diameter perpendicular to the longest diameter in the plane of measurement should be at least 5 mm for the lesion to be considered measurable. Cystic lesions or surgical cavities should generally be considered non-measurable unless there is a nodular component that measures 10mm or more in longest diameter and 5mm or more in the perpendicular plane. The cystic or surgical cavity should not be measured for the determination of a response.

Non-measurable lesions

Non-measurable disease includes all other lesions, including lesions with longest dimension less than 10 mm, lesions with borders that cannot be reproducibly measured, dural metastases, bony skull metastases, cystic-only lesions, and leptomeningeal disease.

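### Section 9.1 does not keep brain lesions out of the RECIST 1.1 assessment behind extracranial PFS, so intracranial change can be scored in that endpoint

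*Combined protocol and SAP*

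**What the plan says.** **Eligibility.** Section 3.1, criterion 5, requires "At least one untreated asymptomatic brain metastasis that is measurable by RECIST 1.1 that has not been previously irradiated".

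**RECIST lesion set.** Section 9.1.3 takes "All measurable lesions up to a maximum of 2 lesions per organ and 5 lesions in total", and these are to be "representative of all involved organs, should be identified as target lesions and recorded and measured at baseline". Sections 9.1.4 to 9.1.7 treat non-target and new lesions without regard to site; any new lesion is progression. Footnote 5 of the study calendar (section 7) describes brain MRI and body CT together as the tumor response assessment.

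**Endpoints that use RECIST.** Extracranial PFS in section 2.2.2 runs "until the criteria for extracranial disease progression is met as defined by RECIST 1.1 or death". For response, "ORR will include complete response (CR) + partial response (PR) as determined by RECIST 1.1". Section 12.2 instead lists PFS as intracranial or extracranial, and section 12.2.2 counts progression in either compartment, using RECIST 1.1 and RANO-BM.

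**CNS assessment.** Section 9.2.2 states: "Assignment of CNS response is independent of systemic disease response". It gives the CNS its own set of up to five targets under RANO-BM. Section 9.2.1 classes as non-measurable "dural metastases, bony skull metastases, cystic-only lesions, and leptomeningeal disease".

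**The concern.** An extracranial endpoint needs a lesion set that leaves out the brain, or a rule for removing it. The plan has neither. A site that follows section 9.1.3 as written will normally enter brain lesions in the RECIST sum, and the same lesions will also sit in the RANO-BM sum.

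Two secondary endpoints are then open to more than one derivation. One brain event could be scored in both iPFS and extracranial PFS, and ORR would combine two compartments without saying so. The protocol's own background (section 1.2) cites a chemotherapy study in which brain response was 27%, lower than the extracranial response, so the mix affects how ORR is read.

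Eligibility has a related mismatch: a patient qualifies on RECIST measurability but is assessed for the primary endpoint under RANO-BM.

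**Working it through.** The plan states no figure on this point to reproduce. The check is a reading of the rules plus arithmetic on the thresholds in section 9.1.5.

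**1. Do brain lesions enter the RECIST set?** Every patient has a measurable brain lesion (3.1), targets must represent all involved organs (9.1.3), and no exclusion appears in 9.1.1 to 9.1.7. Read literally, yes, with at most 2 of the 5 places going to the brain. The five-lesion cap and the reproducibility condition allow occasional exceptions.

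**2. Effect on the sum.** Let b and e be the brain and extracranial sums in mm. Section 9.1.5 sets partial response at -30% from baseline, and progression at +20% from the smallest sum with at least +5 mm. Take b + e as the reference sum in each case.

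- Brain stable, extracranial shrinkage needed for PR: 0.30 × (b + e) / e
- Brain stable, extracranial growth needed for PD: 0.20 × (b + e) / e
- Extracranial stable, brain growth that alone gives PD: 0.20 × (b + e) / b

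The sizes below are assumptions; the 5 mm condition is met in every row.

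| b / e (mm) | Brain share | Extracranial shrinkage for PR | Extracranial growth for PD | Brain growth alone giving PD |
|---|---|---|---|---|
| 10 / 100 | 9% | 33% | 22% | 220% |
| 20 / 80 | 20% | 37.5% | 25% | 100% |
| 30 / 60 | 33% | 45% | 30% | 60% |
| 40 / 60 | 40% | 50% | 33% | 50% |
| Brain excluded | – | 30% | 20% | not possible |

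**3. Two worked cases, also with assumed sizes.**

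- Extracranial 50 mm unchanged, brain 20 to 35 mm: (50 + 35) / (50 + 20) = 85 / 70 = 1.214. That is +21% and +15 mm, so RECIST progression with no extracranial growth.
- Extracranial 60 to 36 mm (-40%), brain 30 mm unchanged: (36 + 30) / (60 + 30) = 66 / 90 = 0.733. That is -27%, so stable disease where the extracranial lesions alone give a partial response.

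Errors therefore run in both directions.

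**4. New brain lesions.** This route does not depend on the brain share. Sections 9.1.5 and 9.1.7 make any new lesion progression. Section 9.2.4 says that on immunotherapy new lesions alone may not be progression, and section 9.2.5 asks for confirmation of early radiographic progression without neurologic worsening. On the literal reading, a new brain lesion could be a RECIST event while it is not yet, or never becomes, an iPFS event. Section 6.4 ends protocol therapy on RECIST 1.1 progression, so the mismatch reaches beyond the secondary endpoints.

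**5. PFS definitions.** Section 2.2.2 counts extracranial progression or death. Section 12.2.2 counts progression in either compartment or death. These are different endpoints, and section 12.6.2 analyses only one, called PFS.

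**6. Measurability.** Section 3.2 (exclusion 2) allows discrete dural metastases, and section 9.1.2 lets cystic metastases count as measurable. Section 9.2.1 makes dural and cystic-only lesions non-measurable. A patient with only such lesions can enter without a RANO-BM target. Section 12.5 then limits efficacy to patients with measurable disease without naming the criterion.

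**The case against.** The strongest reply is that section 2.2.2 already restricts the event to extracranial progression and that section 9.2.2 separates CNS from systemic response. In the 50 mm case above, an assessor guided by section 2.2.2 would record no extracranial event. This stands as evidence of intent. It does not supply a derivation: neither section removes brain lesions from the RECIST target, non-target or new-lesion sets.

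A reader might go further and infer that extracranial PFS and ORR are driven by the brain in every patient. The documents do not support that. A brain lesion in the sum changes a classification only when its share and its change are large enough; at 10/100 mm the thresholds barely move. Nor is a brain lesion in ORR an error, since ORR is an overall rate and is never labelled extracranial.

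A reader might also infer that the data could not be repaired later. Target lesions are recorded and measured, so brain diameters can be subtracted if held lesion by lesion. At least three places remain for extracranial targets, so displacement matters only where more than three would have been chosen. Displaced lesions become non-target, are still followed for unequivocal progression, but need not be measured (9.1.4); for those, scans would have to be re-read.

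On eligibility, a patient without a RANO-BM target can still have an iPFS event through non-target progression, new lesions, clinical worsening or death, and a cystic lesion with a large enough nodular part is measurable under section 9.2.1.

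Finally, the primary endpoint uses RANO-BM, and the secondary endpoints are descriptive estimates with confidence intervals. That limits the consequences without removing the ambiguity.

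**Conclusion.** The point holds as a defect of definition that can misclassify events. Section 9.1, followed as written, places brain change in the RECIST assessment on which extracranial PFS rests. For assumed stable brain shares of 9-40%, the extracranial shrinkage needed for partial response rises from 30% to about 33-50%, and the growth needed for progression from 20% to about 22-33%. The effect may be small or material, and the documents give no lesion sizes to decide which. The new-lesion route applies whatever the share.

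Two further inconsistencies need no assumptions: secondary PFS has two definitions, and eligibility and the primary endpoint use different measurability criteria. How many patients have only dural or cystic-only lesions is not stated and cannot be derived. The primary endpoint's own progression criteria are not in question here. The change should be made, chiefly to protect the secondary endpoints.

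**What to change.** 1. State in sections 9.1.3 to 9.1.7 that, for deriving extracranial PFS, CNS lesions are not RECIST target, non-target or new lesions and are assessed under section 9.2.
2. Reconcile section 2.2.2 with sections 12.2 and 12.2.2 so that extracranial PFS and any-compartment PFS are named, defined and analysed separately.
3. Keep ORR as an overall rate, state which compartments it covers, and report extracranial RECIST response and RANO-BM CNS response beside it.
4. Cite RANO-BM measurability (9.2.1) in inclusion criterion 5, and name the criterion meant in section 12.5.
5. Reconcile section 6.4 with sections 9.1.5, 9.2.4 and 9.2.5 on new brain lesions, and say which lesion set the discontinuation criterion refers to. Which clinical rule applies is for the sponsor to decide.

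The cost is protocol wording and a lesion form that records the compartment of each lesion. Item 1 may mean two RECIST lesion sets, depending on how items 3 and 5 are settled. Item 4 would make some patients ineligible. For patients already enrolled, brain diameters can be subtracted from the recorded sums, with scans re-read only where brain lesions displaced extracranial targets.
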